4.10.2 Handling Missing or Partially Missing Data

Missing or partially missing dates will not be imputed at data level. However, assumptions for missing or partially missing dates for important variables will be made to allow inclusion of appropriate data records in the analyses. In general, the assumptions about the missing or partially missing dates, when needed, are made conservative to avoid overestimation of treatment effect and underestimation of adverse effects.

If a medication date or time is missing or partially missing, so it cannot be determined whether it was taken prior or concomitantly, it will be considered both as a prior and a concomitant medication.

If the partial AE onset date information does not indicate whether the AE started prior to treatment or after treatment, the AE will be classified as after the start of treatment.

4.10.3 Pooling Algorithm

For analysis purposes all participants will be pooled by geographic region, with this same variable then used as a fixed effect in any statistical modeling. The pooling will occur according to the following rule:

Participants will be grouped into their geographic regions defined by the categories North America and Rest of World.

5 SUPPORTING DOCUMENTATION

5.1 Appendix 1 Randomization Approach

The dynamic minimization algorithm described in Pocock and Simon (Pocock et al. 1975) was used to allocate patients to either ACP or Sham in this study. This procedure consists of two steps. First, the level of balance in treatment assignments within 1) the strata of randomization stratification factors (i.e. site) and 2) the overall population are determined for the settings where a new participant is assigned to ACP or Sham. Then, the treatment assignment that would cause the least imbalance is attributed higher probability when assigning the actual treatment assignment to the new participant. Note that this allocation scheme helps balance the treatment assignment while maintaining a random component.

Imbalance measures

Let X_{jk} be the number of participants already assigned to treatment k ($k = \text{ACP, Sham}$) within site j ($j = 1, 2, \dots, S$) as the new participant to be assigned. That is, X_{jACP} and X_{jSham} are the number of participants already assigned to receive ACP and Sham within site j , respectively. Additionally, let Y_{ACP} and Y_{Sham} be the total number of participants already assigned to ACP and Sham across all sites, respectively.

Suppose a new participant is enrolled at Site j . Then, the imbalance in treatment assignments at the site-level is defined by:

$$D_{ACP} = |X_{jACP} - X_{jSham} + 1| \text{ if the new participant is assigned to ACP or}$$

$$D_{Sham} = |X_{jACP} - X_{jSham} - 1| \text{ if the new participant is assigned to Sham}$$

Where $|a|$ is the absolute value of a . Similarly, the imbalance in treatment assignments in the overall population is defined by:

$$T_{ACP} = |Y_{ACP} - Y_{Sham} + 1| \text{ if the new participant is assigned to ACP or}$$

$$T_{Sham} = |Y_{ACP} - Y_{Sham} - 1| \text{ if the new participant is assigned to Sham}$$

The overall imbalance measure is defined by:

$$I_t = W_1 D_t + W_2 T_t \text{ (} t = \text{ACP or Sham)}$$

Where W_1 and W_2 are positive weights that sum to one and are prespecified before the second participant has been randomized. The weights will only be made available to the broader study team after database lock.

Allocation

The first participant will be assigned to ACP or Sham with equal chance. Then, for each subsequent participant, the participant will be assigned to ACP with probability p or to Sham with probability $1 - p$, based on the following rules:

$$p = 0.5 \text{ if } I_{ACP} = I_{Sham}$$

$$p = 0.2 \text{ if } I_{ACP} > I_{Sham}$$

$$p = 0.8 \text{ if } I_{ACP} < I_{Sham}$$

5.2 Appendix 2 Ocular AEs

Ocular AEs are defined as AEs that satisfy at least one of the following criteria:

- 1) The SOC is coded to EYE DISORDERS and (AE location is right and/or left eye or AE term contains Eye or Ocular) or
- 2) The LLT is coded to INTRAOCULAR LENS SUBLUXATION or
- 3) The PT is coded to either INTRAOCULAR PRESSURE INCREASED, INTRAOCULAR PRESSURE DECREASED, INTRAOCULAR PRESSURE ABNORMAL or INTRAOCULAR PRESSURE FLUCTUATED.

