### **3-Day Post-Injection Safety Check ( $\pm$ 1 day)**

- Telephone call to subject to ensure there are no signs or symptoms of retinal detachment or endophthalmitis.

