2.0		4.6.5.1.1	
For shift tables from Baseline to Month 18, it is clarified that the pre-injection assessment will be used, and that these tables will be produced for all ophthalmic examinations.
 
Shift tables from Baseline through Month 18 have been removed.
	
Using the pre-injection assessment will allow more assessments to be included because not all patients will have a post-injection assessment.
 
The information in shift tables from Baseline to Month 18 will already be captured in the shift tables from pre-injection to post-injection.

2.0		4.10.1	Lab and ECG analysis window rules have been updated to differentiate between assessments occurring at early termination visit if the study day is < 534 days or Month 18 if the study day is ≥ 534 days.	Provides a cleaner interpretation of the assessments at Month 18.
2.0		4.10.1	Relaxed the condition for when IOP assessments can contribute to the analysis. Specifically, IOP assessments will now be included if either a pre or post injection record, but not necessarily both, is	Ensures more IOP assessments are included in the analysis.

SAP Version	Approval Date	SAP Section(s)	Change	Rationale
			present on the same day as the IOP assessment.	
2.0		5.1	Expanded the definition of Ocular AEs to include the lower-level term: INTRAOCULAR LENS SUBLUXATION. Additionally, the requirement for AE location to be right/left or both eyes, or AE term to contain eye or ocular has been added.	The exclusion of the lower-level term was a topographic error. The additional requirement is to ensure that the AE either occurred in the eye(s) or its description includes eye or ocular.
2.0		Throughout SAP	Corrected topographic errors without changing contents.	To improve clarity and correct errors.

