- Treatment-emergent SAEs related to injection procedure
- Treatment-emergent SAEs related to study treatment
- All ocular treatment-emergent SAEs for study eye
- Ocular treatment-emergent SAEs related to injection procedure for study eye
- Ocular treatment-emergent SAEs related to study treatment for study eye
- All ocular treatment-emergent SAEs for fellow eye
- Ocular treatment-emergent SAEs related to injection procedure for fellow eye

All AEs, including non-TEAEs, will be included in individual participant listings.

The listings will include the participant identifier, age, sex, verbatim term, SOC/PT, eye (NA/OD/OS/OU), serious (yes/no), date of onset, relative study day of onset, onset before injection, after first injection or after second injection, duration of the event (or continuing), severity (mild/moderate/severe), causality (relationship to study drug/injection procedure), action taken (study drug permanently discontinued: yes/no), treatment (yes/no), and outcome (resolved/not resolved/fatal).

The same listings will be provided separately for SAEs, AEs leading to permanent discontinuation of the study treatment, AEs leading to death and deaths.

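### The ocular-AE definition uses recorded eye location only within SOC Eye Disorders, so eye-located events coded to another SOC are left out of the ocular tables unless they are one of five listed terms

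*SAP*

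**What the plan says.** SAP Section 5.2 (Appendix 2) opens with "Ocular AEs are defined as AEs that satisfy at least one of the following criteria". The three criteria are:

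1. "The SOC is coded to EYE DISORDERS and (AE location is right and/or left eye or AE term contains Eye or Ocular").
2. "The LLT is coded to INTRAOCULAR LENS SUBLUXATION".
3. "The PT is coded to either INTRAOCULAR PRESSURE INCREASED, INTRAOCULAR PRESSURE DECREASED, INTRAOCULAR PRESSURE ABNORMAL or INTRAOCULAR PRESSURE FLUCTUATED".

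Criteria 2 and 3 carry no SOC condition. The SAP version history shows that version 2.0 made two changes to this definition. It added the lens-subluxation LLT, whose absence it describes as an error, and it added the location-or-term condition. The reason given for the latter is: "The additional requirement is to ensure that the AE either occurred in the eye(s) or its description includes eye or ocular".

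SAP Section 4.6.1 plans a set of ocular TEAE and SAE tables, nearly all for the study eye. It also plans a second TEAE overview split into Study Eye, Non-Study Eye and Non-Ocular. The AE listings in the same section carry the affected eye: "verbatim term, SOC/PT, eye (NA/OD/OS/OU), serious (yes/no").

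**The concern.** Criterion 1 joins SOC and location with 'and'. Location can therefore remove an event from the ocular set but can never bring one in. The only way in from another SOC is a closed list of five terms. The list's existence indicates that the authors expected some eye events to code elsewhere, and the version 2.0 correction shows that a list kept by hand can omit a term. The version history treats having occurred in the eye as a mark of an ocular event, yet the rule ignores that mark outside one SOC.

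Safety is part of the trial objective, and treatment is by repeated intravitreal injection. After each injection visit the protocol (Section 10.2) requires a telephone check for "no signs or symptoms of retinal detachment or endophthalmitis". If a complication of this kind coded to another SOC, it would be left out of the tables a reader consults for ocular safety. The omission might not be balanced between arms. Under Protocol Section 17.4 the sham uses a syringe without a needle, so a complication of entering the globe can arise only from active injections.

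**Working it through.** The plan gives no figure to reproduce. The check is of the logic, followed by a count of the tables that depend on it.

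**The rule as written.** Let S = SOC is Eye Disorders, L = an eye is recorded, T = the term contains Eye or Ocular, and N = one of the listed terms (1 LLT + 4 PTs = 5). Appendix 2 gives:

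ocular = (S and (L or T)) or N

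Four yes/no inputs give 2⁴ = 16 combinations. All 8 with N = yes are ocular. The 8 with N = no are:

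| SOC Eye Disorders | Eye recorded | Term has Eye/Ocular | As written | Amended rule |
|---|---|---|---|---|
| yes | yes | yes | ocular | ocular |
| yes | yes | no | ocular | ocular |
| yes | no | yes | ocular | ocular |
| yes | no | no | not ocular | ocular |
| no | yes | yes | not ocular | ocular |
| no | yes | no | not ocular | ocular |
| no | no | yes | not ocular | not ocular |
| no | no | no | not ocular | not ocular |

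As written, 8 + 3 = 11 combinations are ocular and 5 are not. Two of the five are the main problem: the event is recorded in an eye, yet is non-ocular because of its SOC, even when its term contains Eye or Ocular.

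**The amended rule.** With ocular = S or L or N, three combinations change and the other 13 do not. The two that stay non-ocular have neither a recorded eye nor the Eye Disorders SOC, and could not be placed in an eye-specific table anyway.

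**Tables affected.** SAP Section 4.6.1 lists:

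- 6 ocular TEAE tables (all, procedure-related and drug-related, then the same three by maximum severity);
- 3 ocular TEAE tables for study drug discontinuation;
- 3 ocular SAE tables for the study eye;
- 2 ocular SAE tables for the fellow eye.

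The total is 6 + 3 + 3 + 2 = 14. Thirteen name an eye. The other is worded 'for study', apparently a shortened 'study eye'.

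**Size.** The documents do not say how often an eye event codes outside Eye Disorders and off the list. As an assumption only, let r be the risk per participant of at least one such event. With the planned 60 per arm (Protocol synopsis), the expected number affected is 60r and the chance of at least one is 1 − (1 − r)⁶⁰:

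| Assumed r | Expected in 60 | Chance of at least one |
|---|---|---|
| 0.5% | 0.3 | 26% |
| 1% | 0.6 | 45% |
| 2% | 1.2 | 70% |
| 5% | 3.0 | 95% |

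For context, planned exposure is 6 + 15 × 2 = 36 injections per active participant, or 60 × 36 = 2,160 at full compliance (Protocol Section 9.2.3). This does not by itself give r.

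**The case against.** The strongest reply is that no event disappears. SAP Section 4.6.1 also plans tables by SOC and PT with no ocular filter: all TEAEs, those related to the injection procedure or to study drug, those leading to discontinuation, all SAEs and procedure-related SAEs. Every AE is listed with its eye and causality. The ophthalmic examination shift tables and the IOP summaries (Section 4.6.5.1) do not depend on AE coding. All of this stands. A reader might infer that eye events would vanish from the safety report or from the procedure-related tables generally; the documents do not support that.

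Four further limits also stand:

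- **The overview.** Section 4.6.1 points to the ocular definition only for the first ocular TEAE table. It does not say that the Study Eye / Non-Study Eye / Non-Ocular split uses it, so mislabelling there is possible but not certain.
- **Eye Disorders events with no recorded eye.** It is tempting to say that these are all excluded. They are excluded only if the term also lacks Eye and Ocular and is not listed. No definition could place them in an eye-specific table, so this affects only the overview label. The location-or-term condition was also a deliberate choice with a stated reason.
- **Coding of key risks.** A reader might assume that endophthalmitis or injury of the injected eye codes outside Eye Disorders. The documents do not say. Criteria 2 and 3 name only lens-subluxation and pressure terms, and those are already kept.
- **Counts from complication rates.** Multiplying 2,160 injections by a general complication rate would not measure the undercount, because only events coded elsewhere and off the list are lost.

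The reply does not answer the central point: an event recorded in the study eye can be non-ocular solely because of its SOC.

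**Conclusion.** The point holds as a classification gap. Apart from five listed terms, an AE recorded in an eye but coded outside SOC Eye Disorders is left out of all 14 ocular tables. This follows from the text of Appendix 2 and needs no outside source. How many events are affected is unknown. The risks of 0.5% to 5% in the table are assumptions that show scale, and whether the main injection risks are among the affected events must be checked in the MedDRA version in use. With 60 per arm and few serious events to be expected, one reclassified event could visibly change an ocular SAE row, but the documents do not show that this will happen. The handling of Eye Disorders events with no recorded eye is a minor addition.

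**What to change.** Amend SAP Appendix 2 so that an ocular AE is any AE that meets at least one of these:

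- recorded location is the right eye, the left eye or both, whatever the SOC;
- SOC is Eye Disorders, whatever the location;
- the LLT or PT is on the existing list.

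Assign Study Eye and Non-Study Eye from the recorded location, and state that the second TEAE overview uses the same definition. Before database lock, query AEs in Eye Disorders or on the list whose eye is NA. Show any that remain as 'Ocular, eye not specified' in the overview, because they fit neither eye category. Check the MedDRA coding of the injection risks named in the protocol at the same time. Correct the reference in Section 4.6.1, which points to an Appendix B although the definition is in Appendix 2.

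The cost is a short edit to Appendix 2, a small change to the AE derivation, one extra overview category and a limited set of queries. No new data are needed, since the eye is already among the listed AE items. The downside is that a few trivial eye-located events may enter the ocular tables. The change should be made before unmasking.

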5.3 Appendix 3 List of Abbreviations

Abbreviations	Description of abbreviations
ACP	Avacincaptad pegol
ADEG	Electrocardiogram Examinations Analysis Dataset
ADIOP	Tonometry Analysis Dataset
ADLB	Laboratory Test Results Analysis Dataset
ADPE	Ophthalmic Examinations Analysis Dataset
AE	Adverse Event
ANCOVA	Analysis of Covariance
ATC	Anatomic Therapeutic Chemical
BCVA	Best Corrected Visual Acuity
CSR	Clinical Study Report
DDAF	Definite Decrease in Autofluorescence
ECG	Electrocardiogram
ETDRS	Early Treatment Diabetic Retinopathy Study
FA	Fluorescein Angiography
FAF	Fundus Autofluorescence
FE	Fellow Eye
FP	Fundus Photography
GGT	Gamma-glutamyl Transferase
ICE	Intercurrent Event
ICH	International Conference on Harmonization
IOP	Intraocular Pressure
ITT	Intention-to-Treat
J2R	Jump to Reference
LLN	Lower Limit Normal
LLT	Lower-Level Term
MAR	Missing at Random
MedDRA	Medical Dictionary for Regulatory Activities
MI	Multiple Imputation
MMRM	Mixed Model for Repeated Measures
MVN	Multivariate Normal Distribution
NA	Not Available / Not Applicable
OD	Oculus Dexter (Right Eye)
OS	Oculus Sinister (Left Eye)
OU	Oculus Uterque (Both Eyes)
REML	Restricted Maximum Likelihood
PSC	Posterior Subcapsular Cataract
PT	Preferred Term
Q1	1 st Quartile
Q3	3 rd Quartile
SAE	Serious Adverse Event
SAF	Safety Analysis Set
SAP	Statistical Analysis Plan
SAS	Statistical Analysis System
SD	Standard Deviation
SD-OCT	Spectral Domain-Optical Coherence Tomography
SE	Study Eye
SGOT/AST	Aspartate Aminotransferase
SGPT/ALT	Alanine Aminotransferase
SOC	System Organ Class
STGD1	Stargardt Disease 1
TEAE	Treatment Emergent AE
ULN	Upper Limit Normal

Abbreviations	Description of abbreviations
UN	Urea Nitrogen
VA	Visual Acuity
WBC	White Blood Cells
WHO	World Health Organization

